11.2 Sample Size and Accrual

[figure not shown]
The study will enroll 32 patients for the estimates of the dose-toxicity function. Patients will be recruited as available and assigned to treatment according to the estimate probability of DLT as described above. No formal cohort size is required; however, at least two patients must be observed for their entire acute toxicity period (29 days) before dose escalation is allowed.

The operating characteristics of this trial design were evaluated through simulation, both near to and far from our expectations for toxicity. Table 7 lists our prior expectations for toxicity at each dose level and the simulated 'truth' for the four simulation scenarios. The simulation scenarios are: 1 – our prior expectations for toxicity are correct, 2 – our prior expectations moderately underestimate the true probability of toxicity at all dose levels, 3 – our prior expectations moderately overestimate the true probability of toxicity at all dose levels, and finally 4 – our prior expectation severely underestimated the true probability for toxicity. The MTD or RP2D is in gray; the dose level with the highest estimated probability of dose-limiting toxicity not exceeding 0.35.

Table 7. Operating Characteristics for Trial Schema					
Dose Level	Expectation for probability of DLT	Scenario 1	Scenario 2	Scenario 3	Scenario 4
0	20%	20%	20%	15%	45%
1*	27%	27%	35%	20%	60%
2	35%	35%	50%	30%	75%
Other Variables		Scenario 1	Scenario 2	Scenario 3	
Probability of early termination (PET)		17%	32%	7%	
Expected number (EN) of patients treated at MTD		16	12	22	
Probability of selecting correct dose level as MTD		70%	40%	90%	

**starting dose level*

The following figure displays the operating characteristics for this trial design under the four scenarios. The simulations indicate that this design does a good job of choosing the MTD or RP2D and treats a majority of patient at that dose level under scenarios both near to and far from expectations. The trial also stops early and protects the patient from the possibility of unjustifiable probability of DLT when the reality of the probability of DLT is moderately to severely higher than what we expect.

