11.3 Dose Allocation

The dose level for each patient treated on this trial will be determined by the study statistician based upon selecting the dose level with the highest estimated probability of dose-limiting toxicity not to exceed or threshold of 35%, based upon our prior expectation and accumulating trial data; subject to the following constraints:

- The 1st and 2nd patients will be assigned to receive dose level 1
- Intra-subject dose escalation is not permitted
- The dose may be escalated only 1 dose level between adjacently accrued and treated patients. Dose de-escalated between adjacently accrued and treated patients is not restricted.
- At a minimum two patients at a given dose level are required to be completely observed for the DLT observation period (Cycle 1, days 1-28, D1C2 (day 29)) before escalation is allowed.
- Patients will be recruited as available and assigned to treatment according to the TiTE-CRM algorithm. No formal cohort sizes or accrual rate limits are required.

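### Section 11.2 says Scenario 2 underestimates toxicity at every dose level, but Table 7 leaves level 0 at its prior value of 20%, so the stated operating characteristics are not shown to apply to the case described

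*Combined protocol and SAP*

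**What the plan says.** Section 11.2 states that Table 7 "lists our prior expectations for toxicity at each dose level and the simulated 'truth' for the four simulation scenarios". Scenario 2 is the case where "our prior expectations moderately underestimate the true probability of toxicity at all dose levels". Scenario 3 is described with the same reference to all dose levels, but as an overestimate.

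The MTD is the level with the highest estimated DLT probability not above 0.35. Section 11.3 allocates patients on the same 35% limit, starting at level 1. On sample size, "The study will enroll 32 patients for the estimates of the dose-toxicity function".

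For Scenario 2, Table 7 reports 32% early termination, 12 patients expected at the MTD and 40% correct selection. The text then says that the design treats most patients at the MTD both near to and far from expectations. It adds: "The trial also stops early and protects the patient from the possibility of unjustifiable probability of DLT", when true toxicity is moderately to severely above expectation.

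**The concern.** The words and the table describe different scenarios. Level 0 (20 mg, Section 5.1.1) is the only level below the 40 mg start, so it is the only fallback if the start proves too toxic. As tabled, Scenario 2 takes that fallback to be exactly as safe as expected. The only tabled scenario that raises level 0 is Scenario 4 (45/60/75%), where every level exceeds the limit. No tabled scenario has level 0 worse than expected but still within 35%.

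A reader who relies on the description will take 32%, 12 and 40% as the design's behaviour when all levels are moderately more toxic than planned. Correct selection is already only 40%, so a lower figure would matter when judging whether 32 patients are enough.

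**Working it through.** **1. Description against table (Section 11.2, Table 7).**

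| Level | Prior | Scenario 2 | Difference | Scenario 3 | Difference |
|---|---|---|---|---|---|
| 0 | 20% | 20% | 0 | 15% | −5 |
| 1 | 27% | 35% | +8 | 20% | −7 |
| 2 | 35% | 50% | +15 | 30% | −5 |

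Scenario 3 moves all three levels, as its description says. Scenario 2 moves two. This needs no assumption.

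**2. A level-0 value that would fit the description.** Apply the level-1 shift (27% to 35%) to 20%. As a ratio: 20 × 35/27 = 25.9%. As an odds ratio: (0.35/0.65)/(0.27/0.73) = 1.456, and 0.25 × 1.456 = 0.364 in odds, which is 26.7%. I use 27%. Level 1 at 35% is then still the true MTD and level 0 is still within the limit.

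**3. Simulation.** The plan does not give the model, prior variance, accrual rate or numerical stopping rule, so all are assumed. Common to every row: skeleton 20/27/35%, limit 35%, 32 patients, start at level 1, no skipped level on escalation, power model with a normal prior of the SD shown, and a stop when the estimated level-0 rate exceeds 35%. *Partial* means a 29-day window with linear weights and a mean accrual gap of 14 days. *Complete* means each patient is fully observed before the next. There were 2,500 to 5,000 runs per cell, with a standard error up to about 1 point. Cells show early termination % / patients at MTD / correct selection %.

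| Setting | Scenario 2, level 0 = 20% | Level 0 = 27% | Change |
|---|---|---|---|
| Stated in Table 7 | 32 / 12 / 40 | – | – |
| A. Closest to 35%, SD 0.50, partial | 32.3 / 13.2 / 40.9 | 39.4 / 12.3 / 35.6 | +7.1 / −0.9 / −5.3 |
| B. As A, variant of the stopping rule | 34.4 / 12.6 / 38.4 | 40.0 / 12.1 / 34.0 | +5.6 / −0.5 / −4.4 |
| C. Closest to 35%, SD 0.55, partial | 38.1 / 12.0 / 38.3 | 43.6 / 11.4 / 32.5 | +5.5 / −0.6 / −5.8 |
| D. Closest to 35%, SD 0.50, complete | 33.0 / 12.8 / 40.1 | 41.5 / 11.6 / 33.8 | +8.5 / −1.2 / −6.3 |
| E. Highest not above 35%, SD 0.50, complete | 27.4 / 14.4 / 45.3 | 40.0 / 12.5 / 34.9 | +12.6 / −1.9 / −10.4 |
| F. Highest not above 35%, SD 0.60, complete, stop only from 6 patients | 33.3 / 12.4 / 40.2 | 47.4 / 10.5 / 30.6 | +14.1 / −1.9 / −9.6 |

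With level 0 at 25% and 30% instead, setting A gives 37.6 / 12.6 / 37.0 and 42.1 / 12.1 / 33.2. Setting F gives 44.1 / 10.9 / 33.1 and 53.1 / 9.7 / 26.9.

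**4. Fit to the other scenarios.** Table 7 states 17 / 16 / 70 for Scenario 1 and 7 / 22 / 90 for Scenario 3. Setting A gives 15.3 / 18.3 / 66.4 and 5.0 / 23.3 / 87.4, which is near. Setting F gives 21.9 / 14.1 / 45.0 and 9.5 / 20.0 / 72.6, which misses correct selection badly. The smaller changes (A to D) therefore come from the better-fitting settings.

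**5. Could a higher level-0 rate have been simulated?** With the closest-to-35% rule, SD 0.45, complete follow-up and level 0 at 25%, Scenario 2 gives 33.0 / 13.0 / 40.6, about as close to the stated 32 / 12 / 40. Scenarios 1 and 3 give 12.2 / 20.1 / 68.7 and 4.4 / 24.9 / 88.7. Correct selection fits well, early termination runs low and patients at the MTD run high. The stated figures do not settle which level-0 rate was used.

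**6. The closing sentences.** In Scenario 2 the true rates at levels 0 and 1 are 20% and 35%, and both meet the limit. The 32% early termination is thus stopping while an acceptable dose exists. For the majority claim, 12/32 = 37.5%. If the denominator is patients actually treated, the expected total is 0.68 × 32 + 0.32 × m, where m is the mean size at a stop. My complete-follow-up runs gave m of about 9 to 11, hence 24.6 to 25.3 treated and a share of 12/25.3 to 12/24.6, or 47 to 49%. That is about half at best.

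**The case against.** The rates are printed directly above the results, so a careful reader can see what Scenario 2 assumes. The 20% cell may be the slip. If so, the described case was simulated and 32%, 12 and 40% stand. Step 5 shows that this cannot be excluded, so the statement that the described case was never simulated goes further than the documents allow.

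The size of the effect rests on assumed settings, and the largest changes come from those that fit Scenarios 1 and 3 worst. Allocation and MTD selection (Sections 11.3 and 11.4) use the prior and the accumulating data, not the Scenario 2 truth, so trial conduct is unaffected. All of this stands.

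Stopping with an acceptable dose available is also separate from the mismatch. It would hold with level 0 at 25 to 30% too, and it equally describes Scenario 1's 17%. The protection sentence also covers severe excess toxicity (Scenario 4), whose results may be in the figure that was not available to me. That limits the criticism to the moderate case.

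A reader might also infer that the protocol expects Child-Pugh B patients to tolerate the drug worse than planned, which would make Scenario 2 the key planning case. The documents do not say so. Section 1.2 reports a sorafenib database with no significant difference in median daily dose and a conclusion that such patients may be treated safely. The documents support only that safety was evaluated in Child-Pugh A (Section 5.1.1) and that prospective data in Child-Pugh B are minimal (Section 1.2).

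**Conclusion.** The inconsistency is certain from Table 7 alone: the Scenario 2 differences are 0, +8 and +15 points against a description covering all levels. Which of the two is wrong cannot be told from the documents.

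If 20% was simulated, the stated figures are too favourable for the described case. The direction was the same in every setting shown. With level 0 at 27%, correct selection fell by 4.4 to 10.4 points and early termination rose by 5.5 to 14.1. Given simulation error of about a point, that is roughly 4 to 11 and 5 to 14. The size depends on the assumed model, prior SD, dose-choice rule and stopping rule.

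Independently of this, the protection claim does not fit Scenario 2, and the majority claim is not met there. The point should be corrected because it bears on how the design's performance is reported. It does not invalidate the design.

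**What to change.** Check the level-0 rate in the simulation input for Scenario 2.

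- If it was 20%, describe Scenario 2 as underestimation at dose levels 1 and 2 only. Add an all-levels case with level 0 above 20% but not above 35%, and print its early termination, patients at the MTD and correct selection.
- If it was higher, correct the cell in Table 7.

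In either case, state the model, prior variance, accrual rate and stopping rule used in the simulations, so that the figures can be reproduced. Reword the closing sentences: report Scenario 2's early termination as stopping with a dose within the limit still available, and limit the majority claim to the scenarios where it holds, naming the denominator.

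The cost is a look at the existing code, at most one further simulation run, and an edit to Table 7 and its text. If the all-levels case is added, the figures shown will be less favourable.

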11.4 Data Analyses Plans

The TiTE-CRM estimates for the probability of DLT will be reported with 95% Bayesian Credible intervals, once the 32nd evaluable patient has completed the DLT observation period. The MTD/RP2D will be determined at that time as the dose level with the highest probability of DLT not exceeding 35%.

We will record ORR as a yes/no outcome for each patient for the period of active study treatment and report the estimate and exact 95% binomial confidence intervals. We will estimate PFS and OS using the product-limit method of Kaplan and Meier. Follow-up time will be defined as time from date of first study treatment until the date of radiological or clinical progression (leading to withdrawal from the study), or death from any cause, whichever comes first for PFS and for only death from any cause for OS. For patients without events, we will censor the follow-up time at the date of last disease evaluation at the time of analysis. We will report estimates for the median and 75th percentiles with 95% confidence intervals. We will summarize additional safety data (e.g., laboratory safety parameters, vital signs, concomitant medications and new physical examination findings) descriptively by reporting counts and percentages, with exact binomial confidence intervals where appropriate. ORR will be determined as per the RECISTv1.1 guidelines. We will report adverse events per the NCI CTCAE v5.0.

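### Table 7's correct-selection rates for Scenarios 1 and 3 (70%, 90%) are not reproduced by the written 35% rule with the stated 20/27/35% prior, and the summary sentence does not fit Scenario 2

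*Combined protocol and SAP*

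**What the plan says.** Three sections give the same decision rule. Section 11.2 defines the MTD or RP2D as "the dose level with the highest estimated probability of dose-limiting toxicity not exceeding 0.35". Section 11.3 assigns doses by "selecting the dose level with the highest estimated probability of dose-limiting toxicity not to exceed or threshold of 35" per cent. The same sentence says what the estimate rests on: it is "based upon our prior expectation and accumulating trial data". Section 11.4 says of the final analysis: "The MTD/RP2D will be determined at that time as the dose level with the highest probability of DLT not exceeding 35" per cent.

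Table 7 in Section 11.2 gives the prior expectation for DLT as 20%, 27% and 35% at levels 0, 1 and 2. It also reports three operating characteristics for each of the first three scenarios:
- The row "Probability of selecting correct dose level as MTD" has 70% in Scenario 1, then 40% in Scenario 2 and 90% in Scenario 3.
- The row "Expected number (EN) of patients treated at MTD" has, in the same order, 16, then 12, then 22.
- Early termination (PET) is put at 17%, then 32%, then 7%.

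The text then concludes that "this design does a good job of choosing the MTD or RP2D and treats a majority of patient at that dose level", both near to and far from expectations. It describes Scenario 2 as the case in which "our prior expectations moderately underestimate the true probability of toxicity at all dose levels".

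**The concern.** In Scenario 1 the true DLT rate at the correct level, its prior expectation and the limit are all 35%. An estimate centred on the limit should fall above it in many trials, and each such trial names a lower dose or stops. A 70% success rate after 17% of trials have already stopped therefore looks too high for this rule.

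Naming the RP2D is the primary objective, and Table 7 holds the only numeric selection rates in the text available. If the table came from a different rule or prior, anyone judging whether 32 patients are enough is relying on figures for another design. The summary sentence also claims good performance across scenarios, which Scenario 2's own column does not bear out.

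**Working it through.** **Inputs from the documents.** N = 32. Prior expectation 20/27/35%. True rates: Scenario 1 20/27/35% (correct level 2), Scenario 2 20/35/50% (correct level 1), Scenario 3 15/20/30% (correct level 2). Limit 35%. First two patients at level 1. Escalation by one level at a time, after two fully observed patients. DLT window 29 days.

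**What Table 7 implies.** If selection is counted over all trials, correct selection among trials not stopped is selection / (1 − PET):
- Scenario 1: 70/83 = 84%
- Scenario 2: 40/68 = 59%
- Scenario 3: 90/93 = 97%

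**Rough benchmark (not the model estimate).** With all 32 patients at level 2, an observed rate of at most 35% means 11 or fewer DLTs (11/32 = 34.4%). P(X ≤ 11) is 55% at a true rate of 35% and 77% at 30%, before any early stopping.

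**Simulation of the written rule.** In the power model the DLT probability at level i is s_i^exp(b), with s = (0.20, 0.27, 0.35) and b normal with mean 0. Each patient contributes w·p after a DLT (w = 1) or 1 − w·p without one (w = days observed/29, at most 1).

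Assumed, because the documents do not say:
- power or one-parameter logistic model, over a range of prior variances
- accrual of 0.5, 1.5 or 4 patients per month, with uniform DLT times
- stopping when no dose is estimated at or below 35%, allowed from patient 3, 7 or 13, or only at the end

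Of 132 settings screened, the 20 nearest Table 7's PET row were rerun with 3000 trials each (Monte Carlo SE about 0.9 points). Fourteen were within 5 points of that row. All entries are for Scenarios 1/2/3.

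| Rule and prior centre | Correct selection, % | PET, % | EN at MTD |
|---|---|---|---|
| Table 7 | 70/40/90 | 17/32/7 | 16/12/22 |
| Written rule, 20/27/35%, 14 settings | 44-50/40-46/74-79 | 15-21/28-33/5-9 | 12-15/11-14/18-22 |
| Same, coded separately, power SD 0.5-0.55 | 44-48/39-49/73-77 | 14-19/27-34/6-9 | not tabulated |
| Same 14 settings, final selection by closest to 35% | 62-68/34-40/85-90 | as row 2 | as row 2 |
| Written rule, 16/22/30%, other stopping rule*, 4 per month | 65/47/86 | 19/33/8 | 20/11/23 |
| Written rule, 16/22/30%, other stopping rule*, 1.5 per month | 72/48/90 | 12/32/4 | 24/11/27 |

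*Power SD 0.2, stopping on 3 DLTs among the first 6 patients at level 1. This is an assumption made for the check.

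A further coding of the written rule with the stated centre gave about 47/39-48/72-74%. Pooled, Scenario 1 is about 44-50% and Scenario 3 about 72-79%.

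**Variants at the stated centre.**
- Posterior mean or median as the estimate: 47-49/39-47/74-79%.
- Estimates rounded to whole percents: 50-52/42-47/76-79%.
- Selection counted only among trials not stopped: 53-60/58-65/80-84%.
- Rounding with a very tight prior (SD 0.1) reaches 64-65% and 88-89%, but with 0% early termination and 85% in Scenario 2.

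**Closest fits.** Final selection by closest to 35% with the stated centre (power SD 0.5, 1.5 per month, stopping from patient 3) gives 65/40/88% with PET 16/28/6%, a largest gap of about 5 points over the six percentages. The two shifted-centre rows have largest gaps of about 7 and 8 points.

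**Summary sentence, Scenario 2.** Of planned patients, 12/32 = 37.5% are at the MTD. For patients actually treated, if stopped trials average n patients, the denominator is 0.68 × 32 + 0.32 × n = 21.76 + 0.32n. With n = 16 the share is 12/26.88 = 45%; with n = 3 it is 12/22.72 = 53%; the limit at n = 0 is 12/21.76 = 55%. The PET-matched simulations treat up to about 27 patients on average, and 12/27 = 44%. The range is roughly 44-55%.

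**Scenario 2 description.** Level 0 has a true rate of 20% and a prior expectation of 20%, so toxicity is not underestimated there.

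**The case against.** The strongest reply is that the documents never give the working model, prior centre, prior variance, accrual rate or stopping criterion. Treating Table 7's expectation column as the model's prior centre is the natural reading of Section 11.3, but still a reading. The objection has force: with a somewhat lower centre and a different stopping rule, the written rule comes within about 8 points of all six percentages. A reader might infer that no version of the written rule could give Table 7. The check does not support that. Those settings do put about 20-24 patients at the MTD in Scenario 1, against the stated 16, so the fit is imperfect.

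A reader might also infer that the simulations used a closest-to-35% rule. That fits the percentages slightly better, but a good fit does not establish what was run. An unstated stopping rule, another model or an outdated table remain possible.

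The majority claim depends on the denominator. At 44-55% of patients treated it is borderline, so the documents do not support calling it a flat contradiction. Whether 40% correct selection is good is a judgement, though the figure is weak support for the claim.

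Finally, Section 11.2 refers to a figure covering all four scenarios that is not available here. Nothing is made of the absence of Scenario 4 from the lower part of Table 7. The figure's absence does not alter the printed numbers.

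**Conclusion.** The concern holds in this form: Table 7 does not describe the written rule with a prior centred on the stated expectations. On that basis correct selection is about 44-50% in Scenario 1 against 70% stated, and 72-79% in Scenario 3 against 90% stated. The shortfalls are about 20-26 and 11-18 points, well beyond Monte Carlo error. Scenario 2's 40% is attainable. Under that prior centre, and only under it, the chance of naming the correct dose when expectations are right is nearer one in two than seven in ten.

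The result rests on the assumed models, accrual and stopping rule, restricted to settings whose early termination is close to Table 7's. Confidence is high that the stated rule and prior do not reproduce the table; the cause is unknown. The summary sentence is not supported in Scenario 2, and the description of that scenario is inaccurate at level 0. These are wording faults. The whole point should be fixed, but it does not show the design to be unsound.

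**What to change.** 1. Report the working model, prior centre and variance, accrual rate, stopping criterion and final-selection rule behind Table 7, and reconcile them with Sections 11.2, 11.3 and 11.4.
2. Rerun the simulation under the rule and prior that will actually be applied. Restate correct selection, early termination and expected number at the MTD from that rerun, not from the ranges here. Say whether selection is out of all trials or only those not stopped.
3. Reword the summary sentence to match the restated table, giving the denominator for any majority claim, and correct the Scenario 2 description for level 0.

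The cost is a statistician's rerun and edits to Sections 11.2 to 11.4, with no extra patients. If the written rule and stated prior are kept, the Scenario 1 and 3 figures will be less favourable. If a different rule or prior was simulated and is intended, the text of those sections needs an amendment.

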11.3 Dose Allocation

The dose level for each patient treated on this trial will be determined by the study statistician based upon selecting the dose level with the highest estimated probability of dose-limiting toxicity not to exceed or threshold of 35%, based upon our prior expectation and accumulating trial data; subject to the following constraints:

- The 1st and 2nd patients will be assigned to receive dose level 1
- Intra-subject dose escalation is not permitted
- The dose may be escalated only 1 dose level between adjacently accrued and treated patients. Dose de-escalated between adjacently accrued and treated patients is not restricted.
- At a minimum two patients at a given dose level are required to be completely observed for the DLT observation period (Cycle 1, days 1-28, D1C2 (day 29)) before escalation is allowed.
- Patients will be recruited as available and assigned to treatment according to the TiTE-CRM algorithm. No formal cohort sizes or accrual rate limits are required.

